Study sites: Antenatal and postnatal clinics at Mulago Hospital and MU-JHU Research Clinic.

Noting Mulago Hospital is undergoing extensive renovation which may affect client volumes; one or more of KCCA Clinics including Kisenyi Health Center IV, Kawempe Health Centre IV, Komamboga Health Center III, Kawaala Health Center III and Kiswa Health Centre IV and/or China-Uganda Friendship Hospital Naguru and Nsambya Hospital would be added as recruitment sites if inadequate recruitment rates are achieved at Mulago Hospital alone.

Study outcomes

A. Quantitative data outcomes:

[figure not shown]
Primary:

- i) Incidence of one or more STIs during study follow-up, with STIs confirmed by laboratory tests of HIV-1, Neisseria Gonorrhoea, Treponema pallidum (Syphilis), Chlamydia trachomatis, Bacterial Vaginosis or Trichomonas vaginalis.
- ii) Reported (and validated) consistent condom use and uptake of effective contraceptive method
- iii) Acceptability and desirability of assigned clinic service model

B. Qualitative Data Outcomes:

- i) Teen mothers' knowledge, attitudes and practice regarding teen reproductive health and related health services and risk perception and motivation to utilize reproductive health services and use of dual protection methods derived from FGD and single and serial IDIs
- ii) Health providers' knowledge, attitudes and practice regarding provision of adolescent reproductive health services

STUDY SCHEMA

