
*Only at 3 months and study exit (month 9 or 6 for the last participants to enroll), † Pre/posttest counseling and HIV testing done only at 3 months and study exit, ‡ STI lab tests done at study exit and when clinically indicated, ¥done at 36 weeks of gestation for all study groups, ‡ done only at study exit for participants with self-reported consistent condom use

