3.6 Study Endpoints

3.6.1 Quantitative data outcomes

Primary outcomes

1. Incidence of one or more STIs during study follow-up, with STIs confirmed by laboratory tests of HIV-1, Neisseria Gonorrhoea, Treponema pallidum (Syphilis), Chlamydia trachomatis, Bacterial Vaginosis or Trichomonas vaginalis (Composite outcome)
 - New HIV-1 diagnosis by 2 separate HIV tests with negative HIV-1 test at enrollment AND/OR
 - New Neisseria Gonorrhoea, Treponema pallidum (Syphilis), Chlamydia trachomatis, Bacterial Vaginosis or Trichomonas vaginalis test having been negative at enrollment OR with completed treatment if positive at baseline
2. Reported (and validated) consistent condom use and uptake of effective contraceptive method (Composite outcome)
 - Absence of repeat pregnancy (diagnosed by rapid urine pregnancy testing for HCG)
 - Uptake of effective contraceptive method with insertion/prescription by clinic staff from 3 months postpartum to 9 months or study completion (which ever comes 1st)
 - Self-reported consistent use of condoms during penetrative anal or vaginal sex including a) since enrollment b) since last visit c) at last penetrative sex act
 - Absence of Y-chromosome in analysis of vaginal swabs

Secondary outcomes

3. Acceptability/desirability of assigned clinic service model

Acceptability of clinic service model (composite)

- Frequency of visits
- Relevance of information to own life
- Sense of psychosocial support

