3.7 Statistical considerations and analysis plan

3.7.1 Sample size determination

Sample size determination

Sample size for this study was based on the outcomes, uptake of effective contraceptive, or prevalence of STIs, at last follow-up comparing each of the two interventions to the control in this three-arm trial. We assumed the uptake of effective contraceptives and consistent condom use as a composite outcome to be 10% [38] (in control/standard), 30% and 35% at the last follow-up in the two intervention arms. At 80% power, and 5% type 1 error rate, and a 10% loss to follow-up, the sample size in the intervention arms was 100 (each 50), while the control/standard was adjusted to 71; this follows a recommendation by Fleiss et al for multiple-arm trials that control arms have a bigger sample size than the intervention.

For the prevalence of STIs, we assumed 20%[10] in control/standard arm, 10% in the intervention-1, and 8% in intervention-2 at the last follow-up, suggesting an average of 55% reduction in prevalence of STI. With similar power of 80%, 5% type-1 error rate and 10% loss to follow-up, a total of 215 respondents in control/standard arm, and 152 per each of the intervention arms resulting in a total of 519. Since 519 respondents are sufficient to address the objectives of the uptake of effective contraceptives + consistent condom use, we determined that the final sample size for this study will be 519 (215 control/standard arm; 152 per each of the two intervention arms).

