3.7.2 Statistical analysis

Exploratory data analysis will be conducted on all variables including the binary outcomes. Descriptive statistics will be generated providing proportions (percentages) for categorical data, and mean (SD)-for normally distributed data, and median (IQR) nonnormal continuous variables. A consort diagram will also be generated to show the time of enrollment, and follow-up. Bar charts showing the distribution of categorical data will also be generated. Data will be assessed for missingness especially as a result of non-follow-up in this prospective study design. In order to address this concern, a comparison of non-follow-up and those followed up will be done, and propensity scores will be constructed to use as weights in the regression models. For categorical/dichotomous outcomes, we will use Fishers Exact Test or chi-square as appropriate, and will report the respective 95% confidence intervals around point estimates, which offer important interpretation for the trial findings.

Primary outcome-1: Composite measure of consistent condom-use and use of an effective FP method. A comparison of this binary outcome will be conducted at the last follow-up. A log-

binomial regression model will be used to obtain the prevalence rate ratios (PRR) as the measure of effect or association, because the outcomes are greater than 10%. The primary exposure variable is study arm. The two intervention arms will be compared to the control arm in the same model. Potential confounders will be adjusted for, after assessing for interaction of some variables with the study-arm in the association with the primary composite outcome. Respondents from the same facility may be correlated, and so adjustment for potential clustering of observations within the selected facilities will be done.

Primary outcome-2: Incidence of any STI. Kaplan-Meier survival analysis will be conducted to determine differences in the probability of STI infection between study arms. Differences in the KM will be determined by log-rank test. Further analysis will be conducted using Poisson regression models to obtain incidence rate ratios (IRR) comparing the two intervention arms to the control arm in the same model. Potential confounders will be adjusted for, after assessing for interaction of some variables with the study-arms in the association with the incidence of STI. Adjustment for potential clustering of observations within the selected facilities will be done.

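### Section 3.7.2 names no variance estimator or clustering method for the Poisson model of the yes/no STI outcome, and two natural ways of filling the gap give wrong confidence intervals

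*Combined protocol and SAP*

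**What the plan says.** - Section 3.6.1 defines the first primary outcome as "Incidence of one or more STIs during study follow-up". Each woman therefore scores yes or no, however many infections she has.
- The Table 3 footnotes in section 3.5.1 give the timing: "STI lab tests done at study exit and when clinically indicated". HIV is the exception: "Pre/posttest counseling and HIV testing done only at 3 months and study exit".
- Section 3.7.1 sizes the trial on proportions: "we assumed 20%[10] in control/standard arm, 10% in the intervention-1, and 8% in intervention-2 at the last follow-up".
- Section 3.7.2 names Kaplan-Meier curves and a log-rank test first for this outcome, and then: "Further analysis will be conducted using Poisson regression models to obtain incidence rate ratios (IRR) comparing the two intervention arms" to control. For facilities it says that "adjustment for potential clustering of observations within the selected facilities will be done", and it repeats this for the STI model. It also plans propensity-score weights for loss to follow-up in the regression models. It does not say how the Poisson variance is estimated or how clustering is handled.
- The other yes/no primary outcome is given a log-binomial model.
- The Protocol Summary (Study sites) starts with Mulago alone. Seven other named facilities "would be added as recruitment sites if inadequate recruitment rates are achieved at Mulago Hospital alone".

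**The concern.** Ordinary Poisson regression takes the variance of each woman's outcome to equal its mean, p. A yes/no outcome has variance p(1-p). When most events are read at a common exit test, follow-up is about the same for cases and non-cases. The model-based standard error of the log rate ratio is then too large. This would remain even if every arm were tested on exactly the same schedule.

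The clustering sentence does not settle the matter. Facility fixed or random effects leave the Poisson variance in place. Clustering the variance by facility does replace it, but with very few clusters, and that errs in the other direction.

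The Poisson model gives the only adjusted effect estimate named for this primary outcome. The log-rank test supplies a p-value but no effect size and no adjustment. Whether the published interval is too wide, too narrow or about right therefore depends on a choice that the plan leaves open until the data are in hand.

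**Working it through.** **Inputs.** From section 3.7.1: risks of 20% (control), 10% and 8% (interventions); 215, 152 and 152 women; 80% power; 5% type I error; 10% loss. Sidedness is not stated, so two-sided is assumed. After 10% loss, about 194 control and 137 per intervention arm are evaluable.

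**The plan's own figure.** A two-proportion calculation was run with pooled variance, no continuity correction, an intervention-to-control ratio of 1/√2, and 20% against 9% (the mean of 10% and 8%, which is the stated 55% reduction). It gives 197 evaluable controls. Dividing by 0.9 gives 219 control and 155 per intervention arm, or 529 in total, within 3% of 215, 152 and 519. The design is thus sized on the average effect. The 20% v 10% comparison alone falls short of 80% power even with correct variance (see below).

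**Standard error of the log ratio**, each intervention arm against control:
- Model-based Poisson: √[1/(n₀p₀) + 1/(n₁p₁)]
- Binomial, which individual-level robust variance estimates: √[(1-p₀)/(n₀p₀) + (1-p₁)/(n₁p₁)]

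For 20% v 10%, n₀p₀ = 194 × 0.20 = 38.8 and n₁p₁ = 137 × 0.10 = 13.7.
- Poisson: √(1/38.8 + 1/13.7) = 0.3143
- Binomial: √(0.8/38.8 + 0.9/13.7) = 0.2938

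| Risks | Poisson SE | Binomial SE | Excess width |
|---|---|---|---|
| 20% v 10% | 0.3143 | 0.2938 | 7.0% |
| 20% v 8% | 0.3421 | 0.3234 | 5.8% |
| 20% v 20% | 0.2495 | 0.2232 | 11.8% |

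**Wald power.** Power = Φ[(|log RR| - 1.96 × SE used) / true SE].
- 20% v 10%: robust Φ(0.6931/0.2938 - 1.96) = 65.5%; model-based Φ[(0.6931 - 1.96 × 0.3143)/0.2938] = 60.4%.
- 20% v 8%: robust 80.9%; model-based 77.6%.

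With 200,000 simulated trials per setting, power is 69% v 63% (20% v 10%) and 87% v 84% (20% v 8%), so the loss is about 6 and 3 points. With no effect at 20%, simulated type I error is 2.7% model-based and 4.7% robust. A chi-square test, which the log-rank test resembles when events are read at a common exit, has 71% and 88% power.

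**If infections are found before exit.** When a woman's time stops at an earlier diagnosis, the Poisson variance becomes more nearly right. A simulation with 20% risk in both arms assumed follow-up of 7.5 to 12 months and early events at uniform times. Model-based type I error was 2.6% with no early detection, 3.0% with a quarter of events found early, 3.8% with half and 4.8% with all. The documents do not give this fraction, so 6-12% is an upper range.

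**If facilities are the variance clusters.** Simulations used no true clustering, both arms at 20%, a G/(G-1) correction (G = number of facilities) and a normal reference.

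| Facilities | Type I error |
|---|---|
| 2 | about 30% |
| 4 | about 14-15% |
| 8, equal size | about 9% |
| 8, half of women at Mulago | about 13% |

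A separate, smaller simulation (400 trials per setting, 20% v 10%) points the same way. The mean cluster-robust SE was 0.26, 0.28 and 0.29 with 3, 5 and 7 facilities, against about 0.30 for individual-level robust and 0.32 for model-based. With Mulago alone there is one cluster and no such variance can be computed.

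**The case against.** The strongest reply is that the plan nowhere commits to model-based variance. A reader might infer that robust variance has been left out, but the text is only silent. It also plans propensity weights in the regression models, and weighted fits are usually reported with sandwich variance, which would be the remedy. This stands. It does not close the gap, because the plan does not say so, and the clustering sentence could turn that same sandwich into a facility-clustered one.

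Second, the Poisson model is labelled further analysis. The log-rank test comes first, and section 3.7.2 also mentions Fisher's exact or chi-square tests for dichotomous outcomes. None of these uses the Poisson variance. A reader might infer that about 6 points of power are lost on the primary outcome. The documents do not support that: the loss is confined to the Wald test in one model, and 6 points applies only to 20% v 10%.

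Third, the model-based error is conservative and cannot create a false positive. That is true of model-based variance, but not of variance clustered on a handful of facilities. The simulated 9-30% does, however, concern a method that the plan permits without naming.

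Fourth, follow-up varies, because women enrol at any gestation from 28 weeks and exit at 6 or 9 months. A rate with person-time is therefore a legitimate target. This also stands, and robust variance does not require giving it up.

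**Conclusion.** The point holds as an unspecified choice with measurable consequences. If the variance is model-based, the rate-ratio interval is too wide by up to about 6% (20% v 8%) to 12% (no effect). The cost in that model is about 3 to 6 points of Wald power, shrinking as more infections are found before exit. If facilities are the variance clusters, the interval is too narrow, with type I error of roughly 9% to 30% for eight down to two facilities. It would be wrong to conclude that the plan's intervals are definitely too wide, since the direction depends on what is left unstated.

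The figures assume two-sided 5% tests, 10% loss in every arm, the planning risks of section 3.7.1, near-equal follow-up and, in the cluster simulations, no true correlation within facility. This is more than missing detail: two natural readings of the text give wrong error bars on the only adjusted effect estimate for this outcome, and a better method is almost free.

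**What to change.** In section 3.7.2, state that the STI Poisson model uses one record per woman with individual-level robust (sandwich) variance, in weighted and unweighted fits alike. State that facility enters as indicator covariates, with small facilities pooled if cells are sparse, and that the variance is not clustered by facility. Keep the person-time offset if an incidence rate ratio is wanted. Report each ratio with its robust 95% interval.

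The cost is a sentence or two and one software option, with no new data, visits or participants. The small downside is up to seven facility terms on about 64 expected events (194 × 0.20 + 137 × 0.10 + 137 × 0.08 = 38.8 + 13.7 + 11.0 = 63.5), which is why pooling should be allowed for in advance.

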We will conduct a 3-arm, randomized, controlled trial of 519 pregnant adolescents aged 15 through 19 years at enrollment to test the acceptability and effectiveness of two enhanced adolescent friendly reproductive health prevention interventions versus current routine care. In each intervention group, 152 adolescent mothers will be randomized to either the enhanced group peer support education and counseling intervention or to the enhanced one-to-one (individual) peer support education and counseling group with a young, model, peer educator trained to deliver RH education and counseling messages, beginning during pregnancy (≥ 28 weeks) and followed up to 9 months postpartum or study end at or after 6 months (whichever comes first). The control group will consist of 215 adolescent mothers randomized to routine care as provided at Mulago hospital (or the designated health facility) where midwives deliver group sessions during antenatal and postpartum care visits as well as standard PMTCT services including routine opt-out HIV C&T and availability of partner C&T. Syphilis testing should also be routinely provided and treatment provided for infected pregnant mothers and their partners as per local standard of care.

The 3 groups will be enrolled with study visits at 3, 6 and 9 months post-partum however the intervention groups (Arms 2 and 3) will have additional visits at 36 weeks Antepartum, delivery, 6 and 10 weeks postpartum, Quantitative baseline data will be collected on routine demographic characteristics, reproductive history, pregnancy intentions and sexual risk/perceptions and HIV/STI status.

Summarized table 1 of the study schedule and evaluation

	SCR/ ENR	36 weeks APT	Birth†	6 weeks PPT	10 weeks PPT	3 months PPT	6 months PPT	9 months PPT†
Arm 1– Routine Care	X					X		X
Intervention: Enhanced Counseling Education Sessions/Routine care as provided	X			X	X	X	X	X
Behavioral Assessments using IAQ and ACASI	X				X		X	X
Psychosocial Assessment	X					X		X
Obtain/review and update RH and Medical History	X	X	*	*	*	*	*	X
Clinical Examination – Blood Pressure, Weight, Obstetric exam	X	X						
Prescribe contraceptives				X	*	*	*	*
Provide available test results	X	X		*	*	X	*	X
Provide treatment/referral as appropriate	*	*	*	*	*	*	*	*
LABORATORY								
Blood	HIV-1 Serology (rapid tests)	X					X	X
	Syphilis serology RPR (TPAB if positive)	X				€		X
Urine	Protein and Glucose	X	X					
	Rapid test for Gonorrhoea infection	X	*		*	*	*	X

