	Rapid test for Chlamydia infection	X	*		*	*	*	X
	HCG test				*	*	*	X
Pelvic	Rapid test for Trichomoniasis	X	*		*	*	*	X
	Collect Vaginal swab for Bacterial Vaginosis testing	x	*		*	*	*	X
	Collect vaginal swab for testing presence of Y chromosome ‡							X
QUALITATIVE COMPONENT								
Serial In-depth Interview (SIDI)	X				X			X
Focus Group Discussion (FGD)	X							X
Single In-depth Interview (IDI)				*	*	*	*	*

X mandatory, *If indicated, †contact at birth only for the intervention groups, € repeat at 6months if positive at enrolment, ‡ done only at study exit for participants with self-reported consistent condom use,

† month 9 will be the study exit visit for most participants however month 6 may the exit visit for the last participants to enroll hence additional exit evaluations would be done then

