3.5 Study Procedures

Information is provided below and in Appendix I on when each study procedure is to be performed.

Pre-screening:

Study staff may pre-screen potential study participants from the ANC clinic. During these interactions they may explain the study to potential participants and ascertain elements of presumptive eligibility, to be confirmed during screening. These include age of the potentially

eligible participant and her estimated gestational age and lack of diagnosed pregnancy complications. Potentially eligible participants will then be referred to the counselors who will conduct the screening and enrolment procedures, on the same day as the prescreening or a different day depending on how many participants are available on a particular day.

Screening/Enrollment Visit

During the screening and enrolment visit, the participant will provide written consent prior to conducting any screening procedures. Screening for the study involves administering the study eligibility criteria and for participants who do not meet eligibility criteria, screening will be discontinued once ineligibility is determined. Consenting eligible participants will be enrolled and randomized into one of the three arms. The procedures done at the screening and enrolment visit are outlined in the table below.

Table2: Screening/Enrolment Visit

Component		Procedure/Analysis
Administrative: Screening		
 • Eligibility Determination • Obtain written Informed Consent for Screening and Enrolment.
Administrative: Enrollment		
 • Assign Participant ID • Randomization • Update Locator Information • Collect Demographics • Schedule Next Visit • Reimbursement
Behavioral		
 • Baseline Behavioral Questionnaire and ACASI • HIV pre and posttest counseling • Demonstration and Provision of Condoms
Clinical		
 • Collect baseline RH and Medical History • Record any Clinical Events • Perform Clinical Examination (abdominal palpation) • Provide available test results • Provide treatment/referral as appropriate
Laboratory	Blood	 Collect Blood 
  2mls for HIV-1 Serology (rapid tests)  2mls for Syphilis serology RPR (TPAB if positive)

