3.5.2 Behavioral Evaluations

Behavioral evaluations assessed by ACASI and interviewer administered questionnaires include;

- Frequency of unprotected sex (self-report of penetrative sexual intercourse since previous visit)/report of condom use
- Risk behaviors – including any new sexual partners/ encounters, concurrent sexual partners (stable or casual), alcohol/drug use, domestic violence e.t.c.
- HIV/STI risk perception and motivation to utilize RH and pregnancy related services
- Reproductive intentions and family planning
- Male partner/s involvement – presence, cohabitation, economic, psychosocial support, health care support, gender based violence etc

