Potential confounders to be adjusted for in these analyses will include participant characteristics such as age, education level. The primary analyses are the intention to treat; for descriptive analysis, baseline data will be summarized separately by study arm. All the analysis will use STATA version 12

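### The covariate set for both primary outcomes is left open, and baseline STI and HIV status, measured on every woman at enrolment, are not named for adjustment

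*Combined protocol and SAP*

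**What the plan says.** The combined protocol and SAP describes adjustment in three places in Section 3.7.2. For the composite of condom use and contraception it states: "Potential confounders will be adjusted for, after assessing for interaction of some variables with the study-arm". Near-identical wording follows for STI incidence. The section closes with the only named variables: "Potential confounders to be adjusted for in these analyses will include participant characteristics such as age, education level". It also plans an adjustment for clustering by facility. No other covariate is named, and the variables to be checked for interaction are not listed.

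The baseline data are richer than that list. Section 3.1 says: "Quantitative baseline data will be collected on routine demographic characteristics, reproductive history, pregnancy intentions and sexual risk/perceptions and HIV/STI status". In Table 1 of the same section, the tests for HIV, syphilis, gonorrhoea, chlamydia, trichomonas and bacterial vaginosis all carry the mandatory mark at enrolment (key: "X mandatory, *If indicated").

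Baseline status also enters the STI endpoint. Section 3.6.1 counts a new non-HIV infection only when there is a "test having been negative at enrollment OR with completed treatment if positive at baseline", and a new HIV diagnosis only after a negative enrolment test. HIV-positive women may be enrolled (Section 3.4.3.2). Section 3.4.5 describes random-sized blocks and names no stratification factor.

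**The concern.** A baseline measurement of the endpoint itself is usually among the first covariates a trial statistician would want in the model. Here it exists for every woman, yet the plan commits only to two demographic examples. Two things are at stake.

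- **Precision and chance imbalance.** If baseline infection predicts later infection, leaving it out makes the arm comparison somewhat noisier. An uneven split between arms then passes straight into the unadjusted ratio.
- **Discretion.** An open list, combined with interaction checks on unnamed variables, allows the model for both primary outcomes to be settled after the results are visible. That is the firmer part of the point, because it does not depend on how strongly baseline infection predicts follow-up infection.

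**Working it through.** **1. The plan's own sample size.** Section 3.7.1 gives 20% in control, 10% and 8% in the interventions, 80% power, 5% type 1 error, 10% loss, and 215 + 152 + 152 = 519. With allocation k = 152/215 = 0.707 and p̄ = (p1 + k·p2)/(1 + k), the control-arm size is

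n = [z_α√((1+k)p̄(1−p̄)) + z_β√(k·p1(1−p1) + p2(1−p2))]² / [k(p1−p2)²].

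- Two-sided 5%, 20% versus the mean intervention rate of 9%: 197 and 140 evaluable, and 219 and 156 after dividing by 0.9.
- One-sided 5%, 20% versus 10%: 192 and 136 evaluable, and 214 and 152 after dividing by 0.9.

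Both are within 3% of 215 and 152. The plan does not state sidedness, so the documents do not settle which was used. Neither calculation includes covariates, so the covariate list has no bearing on 519.

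**2. Power before any adjustment (20% versus 10%, two-sided 5%).** Evaluable women: 215 × 0.9 ≈ 193 and 152 × 0.9 ≈ 137.

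- Pooled rate = (193 × 0.20 + 137 × 0.10)/330 = 0.1585.
- SE under no difference = √(0.1585 × 0.8415 × (1/193 + 1/137)) = 0.0408.
- SE under the planned difference = √(0.16/193 + 0.09/137) = 0.0386.
- Power = Φ((0.10 − 1.96 × 0.0408)/0.0386) ≈ 69.8%.

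For 20% versus 8% the same calculation gives 87.1%.

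**3. Gain from adding baseline STI.** Simulation: 3,000 trials per scenario; 193 versus 137 women; Poisson model with robust standard errors, with and without baseline STI. Baseline prevalence is 20.6%, the Kampala adolescent figure in Section 1.1. All women are treated as at risk. The risk ratio R linking baseline to follow-up infection is not in the documents, so it is varied.

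| R (assumed) | Power without | Power with | Gain in points | Fall in SE |
|---|---|---|---|---|
| 2 | 69.5% | 69.6% | 0.1 | about 1% |
| 3 | 69.3% | 70.9% | 1.6 | about 2% |
| 4 | 69.8% | 74.0% | 4.2 | about 4% |

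Simulation error on each power figure is about √(0.7 × 0.3/3000) = 0.8 points. Type 1 error stays near 5% with or without the covariate.

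**4. Size of chance imbalance.** For baseline prevalence between arms of 215 and 152, SE = √(0.206 × 0.794 × (1/215 + 1/152)) = 0.0429, so the 95% limit is 1.96 × 0.0429 = 8.4 points. An imbalance of that size multiplies the unadjusted ratio by [1 + (R−1) × 0.248]/[1 + (R−1) × 0.164]:

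- R = 2: 1.248/1.164 = 1.07
- R = 3: 1.496/1.328 = 1.13
- R = 4: 1.744/1.492 = 1.17

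At R = 3, a true ratio of 0.50 would appear as 0.50/1.13 = 0.44 or 0.50 × 1.13 = 0.57, depending on direction. This is the edge of what chance produces; a typical imbalance does less.

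**5. The composite outcome.** Section 3.6.1 builds it from absence of repeat pregnancy, contraceptive uptake from 3 months postpartum, consistent condom use, and absence of Y-chromosome. In women enrolled while pregnant, the first two have no baseline counterpart, and the swab is taken only at exit. Only condom use can have a baseline form. That it is recorded at enrolment is an inference: Section 3.5 lists "Baseline Behavioral Questionnaire and ACASI", and the item in Section 3.5.2 reads "self-report of penetrative sexual intercourse since previous visit)/report of condom use", a recall period that has no meaning at a first visit. No gain is calculated for this outcome because the documents give no input for one.

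**The case against.** The strongest reply is that the list is introduced as examples, so nothing stops the analyst from including baseline STI, HIV status or condom use. That is correct. A reader might infer that the plan excludes them; it does not. What remains is that permission is not commitment, and an open list is the source of the discretion.

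A reader might also infer that the comparison is biased. The documents do not support this. Women are individually randomised, type 1 error is near 5% either way, and chance imbalance is ordinary sampling variation that the confidence interval already covers.

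It can further be said that baseline infection is partly handled by the endpoint definition, and that treating curable infections in the woman and her partner (Section 3.5) could weaken the link to later infection. That is fair, and it is why R = 2, with almost no gain, belongs in the range. Likewise, a covariate for HIV status does not settle who is at risk of incident HIV; that is a matter of endpoint definition.

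Two more inferences should be resisted. Age and education cannot be called weak predictors on this evidence: Section 1.1 reports HIV prevalence of 1.6% at 15–17 years and 5.1% at 18–19. And baseline condom use is not the baseline value of the composite, only of one component.

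Finally, Section 3.7.2 lists Kaplan-Meier and the log-rank test first for STI and Poisson regression as further analysis. Covariates in the Poisson model alone would leave the log-rank test unadjusted. That objection stands, and the fix has to cover it.

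**Conclusion.** The point holds as a gap in pre-specification with a modest cost in precision. The plan commits to age and education as examples only, and does not name the baseline test results that it collects on everyone and that enter the STI endpoint definition. The gain from naming baseline STI is about 0 to 4 power points on a base of about 70% for the 20% versus 10% contrast. This rests on an assumed baseline-to-follow-up risk ratio of 2 to 4, a baseline prevalence of 20.6%, and all women being at risk. The 70% itself is a sample-size matter that covariates do not repair, and it applies to the weaker of the two contrasts. For the composite, the case rests on fixing the list in advance; no gain can be quantified.

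**What to change.** Before analysis, replace the open list in Section 3.7.2 with a closed one and drop the data-driven choice of confounders.

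- **STI, Poisson model:** baseline any-STI, baseline HIV status, age and education.
- **STI, log-rank test:** stratify by baseline any-STI, so that both STI analyses use it.
- **Composite, log-binomial model:** age, education and baseline condom use, provided the enrolment questionnaire records it. The sponsor should confirm the item and its recall period, and the plan should describe it as the baseline form of one component only.
- **Convergence:** Section 3.7.2 gives no fallback. State that Poisson regression with robust variance will be used if the log-binomial model does not converge.
- **Interactions:** name the variables to be examined and report them separately, so that they do not decide the content of the primary models.

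The cost is negligible: a few extra model terms and some wording. The enrolment tests are already done in every arm, and no visit, test or sample size changes.
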